2. Country-Level Activities

EGPAF and SAATHII have strong expertise in implementing innovative service delivery models and will provide training, supportive supervision, job aids, and standard operating procedures (SOPs) to health care workers who are engaged in the care of pediatric patients at CaP TB facilities. The goal of these activities is to support the strengthened uptake of current recommendations on TB screening, diagnosis and treatment as well as allow for decentralization and integration of pediatric TB care. CaP TB will also provide training to strengthen completion of TB registers, and may develop other M&E tools to improve the documentation of pediatric TB. EGPAF and SAATHII will also assess and provide SOPs and infrastructure upgrades to improve infection control. EGPAF and SAATHII will support innovations to improve service delivery including creating facility-specific TB champions to monitor service quality, regular performance feedback to facilities, and work with civil society to identify areas to improve care.

Specific packages of activities will vary by country and will be determined based on (1) national policies and guidelines; (2) planned and existing activities supported through other efforts; and (3) country-specific pediatric TB burden and barriers and bottlenecks. For Country Submission- refer to country specifics.

In general, country-level activities will include:

- Decentralizing and integrating delivery of pediatric TB care (diagnosis, treatment (where feasible), and prevention) into MNCH, HIV, nutrition and other key pediatric entry points at the facility level;
- Supporting community-level contact tracing and screening of pediatric contacts for index patients with active TB and where feasible according to MOH guidance, initiation of preventative TB therapy at the community level;
- Documenting and generating evidence for innovative models of care through M&E;
- Strengthening data systems through support for improved use of current registers as well as introduction of new data tools where gaps exist (e.g. for tracking of TB preventative therapy completion in some countries);
- Supporting rapid uptake through trainings, site monitoring and mentorship and strengthening sample transport and referral systems of new diagnostics and medicines that are included in WHO guidelines and are either included in country guidelines or are in the process of being incorporated into national guidance, such as:

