In each site, trained data collectors will retrospectively extract data from appropriate registers, logs, and in some cases patient files, for a period of 12 months starting 6 or more months before the start date of data extraction. This time frame has been selected in order to allow to accurately measure indicators on treatment completion for both drug-sensitive TB treatment and preventive therapy (treatment lasts 6 months in both cases). In certain cases, the data sampling frame will start more than 6 months before the data extraction if CaP TB interventions had started during the sampling frame. Thus the sampling frame was chosen so that the end date of retrospective pre-intervention data abstraction would be before the start of any intervention to ensure that the baseline data was not affected by the early activities. For some indicators, baseline data will not be available in existing registers or logbooks. Data collectors will extract data from all pediatric entry points within the facility, including MNCH, HIV, nutrition and other relevant pediatric health care entry points. Only required variables will be abstracted and entered into the password-protected computers. Data with the patient date of birth (DOB), patient ID (if any), TB treatment ID and preventive treatment ID will be collected. The patient ID (if any), TB treatment ID and preventive treatment ID will all be encrypted before being uploaded into the CaP TB Database Entry Tool. DOB will be abstracted in order to facilitate tracking across registers if needed, as well as for data quality assurance purposes. This information will only be used to link registers. Only de-identified patient data will be abstracted into our global project

database. No other unique identifiers such as contact details of the children or their caregiver will be abstracted from the registers. Data from included pediatric patients will be extracted from the registers and recorded in the CapTB Baseline Data Abstraction form from where the data will be entered into a CaP TB Database Entry Tool (Excel-based and/or Web/mobile App-based) developed for pre-and post-intervention data , in a password protected computer and/or Android device (See Annex A: CapTB Information System).

The target population for the pre-intervention assessment is the records of any pediatric patient (0-14 years of age) who attend one of the sub-set of pilot sites in any of the 10 CaP TB countries who receive TB services. TB services include:

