Data collectors will also collect the ICF tools from the various entry points and collate aggregated data using an ICF data abstraction tool (Attachment B: Pediatric TB Intensified Case Finding Screening Data Abstraction Tool) which will be entered directly into the electronic data entry form. Data collectors will also extract information, such as date of treatment completion, from the TB treatment and TB preventive therapy registers. In the pilot phase (years 1 and 2), data collectors will visit sites frequently for data extraction (approximately every 4-6 weeks). In the expansion phase (years 3 and 4), data collectors will visit sites less frequently for data extraction (approximately every 1-3 months).

Data collection when the project-specific data collection tools are not used

If the CaP TB Pediatric TB Form is not completed or the country does not support use of the ICF Tool and/or CaP TB Pediatric TB Form for all or part of the data collection, data collectors will extract data from relevant sources such as existing registers and logs as in the pre-intervention baseline data collection phase. An indicator mapping exercise will first be conducted to identify the location and source of all required data. This indicator mapping exercise is expected to inform the data collection process which will take place on site, at the project facility. Data will be extracted from the source register or log and, recorded in the baseline data abstraction tool and entered into the CaP TB Database Entry Tool developed for pre-and post-intervention data. Only data required for the project M&E activities will be extracted and will be the same data collected through the CaP TB Pediatric TB Form. EGPAF will closely monitor data collection activities of any country team that cannot use the CaP TB Pediatric TB Form to ensure high quality data is collected. All data collection tools and processes will be approved by the in-country IRB.

A. [Table 1. Indicator Outcomes and Data Sources](#)

This table presents an example of data sources. Specific data sources may vary from country to country. All country-specific data sources will be approved for data extraction by the local IRB.

Primary Outcomes	Data Source Pre-Intervention	Data Source Post-Intervention

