Number and proportion of screened negative pediatric contacts eligible for preventive therapy	TB registers/logbooks Contact tracing forms and registers if available	CaP TB Pediatric TB Form And/or TB registers/logbooks Contact tracing forms and registers if available
Number and proportion of pediatric patients started on preventive therapy of those who are eligible for preventive therapy	TB preventive therapy register	CaP TB Pediatric TB Form And/or TB preventive therapy register
Number and proportion of pediatric patients on preventive treatment who completed therapy	TB preventive therapy register	TB preventive therapy register And/or TB preventive therapy register

B. Table 2. Additional Indicator Outcomes and Data Sources

Additional data will be collected during the pre-intervention phase and will be used to estimate project targets. This table presents an example of data sources. Specific data sources may vary

from country to country. All country-specific data sources will be approved for data extraction by the local IRB.

Primary Outcomes	Data source
Number of HIV positive children (0-14 years) in care	HIV clinic register
Number of adult TB cases notified (disaggregated by age, sex, type of TB [PTB smear positive, PTB smear negative; EPTB], new or previously treated case, DS or MDRTB case)	TB treatment Register
Number of pediatric household contacts recorded for each adult TB case (disaggregated by age, sex)	TB register or TB contact tracing register In countries where information is not recorded in the above described register, there might be the need to extract this information from a sample of patient forms
Number of HIV positive pregnant women in care (disaggregated by age)	PMTCT register
Number of HIV+/TB pregnant women (disaggregated by age, type of TB [PTB smear positive, PTB smear negative; EPTB], new or previously treated case, DS or MDRTB case)	PMTCT register

VII. Use of data generated through CaP TB program evaluation to perform secondary analysis

A. Use of CaP TB Program evaluation data to inform cost-effectiveness analysis

Data documenting the costs and cost-effectiveness of pediatric TB interventions remains limited^{xxxv, xxxvi}, and this represents one of the contributing factors to the under-funding of childhood TB programming^{xxxvii}. The data generated through the TIPPI evaluation are well placed to inform the cost-effectiveness assessment of the package of pediatric TB interventions implemented under the CaP TB project.

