To this aim, EGPAF will sub-contract University of Sheffield, key leader in childhood TB health economic modelling, to perform a cost-effectiveness analysis (CEA). The resulting effects estimates will be based on routinely collected project intervention country-level aggregates from key indicators describing the cascade of care, as well facility-level data for the comparison of the pre- and post- project intervention phase. All data to be used will have already been collected through TIPPI Pre-Intervention evaluation (described in section V, subsection A) and CaP-TB implementation evaluation (described in section V, subsection I).

Only aggregated clinical data will be shared with University of Sheffield and thus considered for the CEA analysis, as described below:

- i. Averaged monthly rates per site (including absolute numerator and denominator) of pediatric (children aged 0-14 years) TB notifications, DS-TB initiations, and PT initiations for a subset of sites for which both baseline and prospective data have already been collected (restricting to sites where data on both periods are available).
- ii. Country-aggregated project intervention numbers of: a) Children screened for TB, b) Children identified as presumptive TB, c) Children with presumptive TB tested with Xpert, d) Children diagnosed with TB, e) Children treated for DS-TB, f) All TB index cases for whom successful contact tracing has been done, g) Children started on TB Preventive Therapy (disaggregated by HIV and Contact investigation entry points), and h) Sites contributing to the country-level dataset.

All patient-level indicators mentioned in points i and ii above are included in Table 1. The cost-effectiveness analysis will use pre-intervention and project intervention data, with the potential for sub-analysis of shorter targeted period during the intervention phase.

The final cost-effectiveness analysis outcomes are expected to be reported by country, and individual countries will be identified to allow to use context-specific results to inform decision-making.

The costs will be estimated as follows:

- Core health services costs will be derived from published literature.
- CaP TB intervention costs will be estimated based on EGPAF CaP TB budgets and expenditure data from EGPAF's financial system.
- EGPAF country team staff will assist in allocating cost items to specific activities within the CaPTB cascade of service delivery.

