Project data sample size: As this is a project evaluation, no specific sample size has been calculated. However, we estimate that the project will increase case detection by 2-fold and result in an additional 16,471 pediatric TB cases being treated.^{xxxix} This is based on an assessment of the number of children we project to screen (both HIV positive and HIV negative) in our project sites throughout the project. From the literature, we estimate that approximate Number Needed to Screen (NNS) to identify 1 TB case is 41 children. Assume that Number Needed to Screen (NNS) to identify 1 TB case is 41 (estimated NNS when symptom based screening is the only primary screening done)^{xl, xli}. Preventive treatment coverage is estimated to increase by four-fold, with an additional 52,317 children to be initiated on preventive therapy. This is based on the estimated number of child TB contacts we will identify through contact tracing plus HIV-infected children who qualify for preventative treatment.

To compare pre- and post-intervention outcomes, we will use either the ratio of the two proportions (relative risk) or the difference between the two proportions (risk difference). We will use Z-tests to assess the statistical significance of the estimated effect of CaP TB.

For measuring turn-around-time (TAT) between when a child is identified as a presumptive TB case and when the child is diagnosed with TB and the TAT between when a child is diagnosed as a presumptive TB case and when the child initiates TB treatment, if the TATs are approximately normally distributed, we will use the paired t-test to assess for statistical significance, otherwise we will use the Wilcoxon rank sum non-parametric test.

A. Quality Assurance

All data collectors will be trained in quantitative data collection by EGPAF staff. Prior to training, all data sources, abstraction and collection tools and procedures will be reviewed and tested. The HQ EGPAF team will provide on-going support to in-country teams throughout program implementation and all data collection activities.

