Data abstracted or collected for this evaluation will be used to 1) Estimate project targets; 2) evaluate the effect of CaP TB as compared to standard of care pediatric TB services as well as to 3) assess the effects of CaP TB during the continued scale up phase (years 3 and 4). Data will be abstracted/collected, analyzed and reviewed on a routine basis to inform program implementation and quality improvement activities, target setting and adjustments, internal and external reports, abstracts, presentations and international guidelines.. Findings will be shared across the project countries, with MOHs, with other implementing partners, with Unitaaid and the WHO and the international community through semi-annual reports to the funder (Unitaid), grey literature, and publications in peer-reviewed journals, meetings and presentations. In order to perform cost-effectiveness analysis, aggregated clinical data will be abstracted and shared with University of Sheffield. Unpublished data analysis and databases might be shared with WHO and with WHO’s collaborators that will be commissioned to compile and assess the evidence needed to support revisions of guidelines and policy formulation. Findings will also be shared through EGPAF data dashboards and website.

Data presented as part of study findings in papers or at conferences will not include any participants' names, IDs or study identifiers. Only the names of project countries will remain identifiable if required.

XIII. Problems Anticipated

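### Section IX does not limit each indicator's pre/post comparison to sites measured in both periods, so a difference in site mix could appear as a programme effect

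*Combined protocol and SAP*

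**What the plan says.** - **Baseline gaps.** Section V.A states "For some indicators, baseline data will not be available in existing registers or logbooks". It does not name the indicators, countries or sites. It allows extraction from registers, logs and "in some cases patient files".
- **An example of a gap.** The country-level activities in Section IV.A.2 include "introduction of new data tools where gaps exist (e.g. for tracking of TB preventative therapy completion in some countries".
- **Importance of that indicator.** Section V.A names four key indicators for judging impact. One is "Number and proportion of pediatric patients on preventive treatment who completed therapy". Table 1 gives the TB preventive therapy register as its pre-intervention source, but the table carries the note "This table presents an example of data sources. Specific data sources may vary from country to country".
- **Scope of the comparison.** Secondary objective a (Section II.B.2) places the comparison with baseline in a subset of project sites. It does not define the subset for each indicator.
- **Analysis.** Section IX says "To compare pre- and post-intervention outcomes, we will use either the ratio of the two proportions" or their difference, with Z-tests. It does not say which sites enter, gives no pairing or stratification by site, and has no rule for an indicator whose baseline is incomplete.
- **The safeguard elsewhere.** For the monthly site rates supplied to the cost-effectiveness analysis, Section VII.A adds "restricting to sites where data on both periods are available". Those rates cover TB notifications, treatment initiations for drug-sensitive TB, and PT initiations. PT completion is not among them.

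**The concern.** A before/after contrast of two proportions is interpretable only if the same sites supply both. If a pilot site or a whole country has no baseline for an indicator, it adds nothing to the pre proportion but can still add to the post proportion. The contrast then combines the change within sites with the difference between sites that did and did not record the indicator beforehand. Section IV.A.1 says that sites were deliberately chosen to be diverse in level, entry point, geography and population, so differences between them are to be expected.

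The results are meant to inform national programmes and international guidelines (Section XII). An effect estimate that partly reflects site mix could mislead those readers in either direction.

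**Working it through.** **Plan's own figures.** Table 3 gives up to 20 baseline sites and up to 70 intervention sites per country: 20 × 10 = 200 and 70 × 10 = 700, as stated. No sample size or power is given, so there is nothing further to reproduce.

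**Formula.** For one indicator, let M be the sites with a baseline and U the sites without one that are included in the post data. Let u be the share of the post-period denominator that comes from U. If no site changes and relative volumes within M are constant:

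- pre = p(M)
- post = (1 − u) × p(M) + u × p(U)
- spurious difference = u × [p(U) − p(M)]

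**Illustration 1 (all values assumed): PT completion, u = 0.5.**

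- p(M) = 80%, p(U) = 60%: post = (80 + 60)/2 = 70%. Difference −10 points, relative risk 70/80 = 0.875.
- p(M) = 60%, p(U) = 80%: post = 70%. Difference +10 points, relative risk 70/60 = 1.17.

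No site has changed in either case. The sign depends only on which group kept the register.

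**Illustration 2 (assumed): pilot sites only, baseline present in k of 10 countries, equal country volumes.** Here u = 1 − k/10, and d is the difference between countries without and with a baseline.

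| k | u | d = 10 points | d = 20 points |
|---|---|---|---|
| 5 | 0.5 | 5 | 10 |
| 7 | 0.3 | 3 | 6 |
| 8 | 0.2 | 2 | 4 |
| 9 | 0.1 | 1 | 2 |

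The spurious shift runs from 1 to 10 points even when expansion sites are excluded.

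For a rough idea of how often a Z-test would call this significant, assume two-sided 5%, 70% completion where a baseline exists, 200 × 5 = 1,000 children post and 1,000 × k/10 at baseline. The 5 per site borrows Table 3's minimum for children with presumptive TB and is used only for scale. Rejection probabilities, over both signs of d:

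- k = 5: 97–99% for d = 20 and 49–54% for d = 10
- k = 9: 15–16% for d = 20 and about 7% for d = 10

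These treat children as independent.

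**With the Section VII.A rule applied to each indicator.** Now u = 0, so the difference above is 0 by construction.

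**What that rule leaves.** Take two matched sites at 80% and 60%, with w the first site's share of the denominator. The crude proportion is 80w + 60(1 − w) = 60 + 20w. If w changes between periods, the crude proportion moves by 20 points × the change in w although neither site has changed. Matching alone is therefore not enough; the estimate must also be stratified by or adjusted for site.

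**The case against.** **Secondary objective a already limits the comparison.** This has force. If the subset means the pilot sites, expansion sites fall outside the pre/post contrast. A reader might infer from Table 3 that most post-period sites lack a baseline: (700 − 200)/700 = 71%, or (700 − 100)/700 = 86% at 10 baseline sites per country. Those percentages do not describe the planned comparison; they apply only if expansion sites enter despite objective a. But objective a does not work indicator by indicator: a pilot site with no baseline for one indicator remains in the subset.

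**PT completion may have a baseline everywhere.** It is tempting to read Section IV.A.2 as saying that some countries have none. The documents do not go that far. A gap in tools need not mean no data, patient files are sometimes used, and Section V.A says that the baseline window was chosen so that completion could be measured. Nor does Table 1 contradict this, since it is labelled an example. What stands is Section V.A's admission about unnamed indicators.

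**Measurement need not change between periods.** A reader might assume that new project tools supply all post data. Section VI uses existing tools where possible, Table 1 gives the PT register for completion in both periods, and the availability caveat on contact-tracing registers appears in both columns. This weakens an argument from changed tools, but not the missing rule on sites.

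**Section IX does not say that sites are pooled across countries.** True. In a country-by-country analysis, a country with no baseline has no comparison rather than a biased one; an indicator with no baseline anywhere likewise permits none. But Section IX does not specify a by-country analysis either, and gaps at some sites within a country would still matter.

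**The scale-up wording.** Section XII plans to "assess the effects of CaP TB during the continued scale up phase (years 3 and 4"). This is listed separately from the comparison with standard of care and states no baseline contrast, so it is a minor point of wording.

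**Conclusion.** The concern holds as a gap in the analysis rule. The plan admits incomplete baseline data for unlisted indicators, and Section IX does not restrict each comparison to sites measured in both periods, although the plan does so in Section VII.A for a different purpose. As written, site mix could appear as a programme effect.

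The documents fix neither size nor direction. The relative risks of 0.875 and 1.17, and the shifts of 1 to 10 points, rest on assumed completion levels, volumes and baseline coverage. A reader might suppose that sites with existing registers were the better-organised ones, so that bias would run one way. Nothing in the documents supports this, and the argument needs only that sites differ. The extent of any gap for PT completion is unknown.

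The point is of moderate weight: it should be settled before the pre/post analysis, and it needs no new data.

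**What to change.** In Section IX:

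1. Apply the Section VII.A restriction to each indicator. A site enters a pre/post comparison only if it has both numerator and denominator in both periods.
2. Estimate the effect stratified by or adjusted for site, for example with a Mantel–Haenszel relative risk or risk difference, so that shifts in site volume do not bias it. Country can serve where site strata are unworkable, but it leaves volume shifts within countries.
3. Report the number of matched sites and countries beside each estimate, and list the indicators and countries with no baseline.
4. Report indicators or sites without a baseline, including expansion sites, descriptively and without an effect claim. If convenient, align the Section XII wording on years 3 and 4.

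**Cost.** A few sentences in the plan, a filter and a stratified estimator. Some indicators will have fewer sites and less precision, and claims will be limited to matched sites.
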